## 7.5 Coding Systems and Conventions

### 7.5.1 Coding of Adverse Events and Medical History

All medical terms reported as adverse events (AE) and as medical history/concomitant disease are coded according to the Medical Dictionary for Regulatory Activities (MedDRA) version in effect at the time the database is closed. At least the System Organ Class (SOC) as well as the Preferred Term (PT) should be available for the statistical analysis. Within each SOC and PT, AEs are graded using the CTCAE grades (Version 5.0) and accompanied by descriptions of severity (Grade).

### 7.5.2 Separation of Medical History from Concomitant Diseases

Separation of medical history from concomitant diseases will be done by comparison of the stop date of the medical condition with the date of the first treatment with study medication. Each finding will be allocated unambiguously either to medical history or concomitant disease.

- **Medical history:** If the stop date is before start of treatment or the stop date is partially given and unambiguously before start of treatment, the medical condition is allocated to medical history. Furthermore, if the stop date is missing and the medical condition is not known to be ongoing, findings coded as “Surgical and medical procedures” are also allocated to medical history.

- **Concomitant diseases:** If the stop date is at or after start of treatment or the medical condition is ongoing, the medical condition is referred to as concomitant disease. If the stop date is partially given and not unambiguously before start of treatment, the medical condition is allocated to concomitant diseases. If the stop date is missing and the medical condition is not known to be ongoing, the medical condition is allocated to concomitant diseases.

### 7.5.3 Coding of Medications

All medications are coded according to the Anatomical Therapeutic Chemical (ATC/DDD) classification system in effect at the time the database is closed. At least the ATC levels 2 and 3 should be available for the statistical analysis.

### 7.5.4 Separation of Previous and Concomitant Medications

Separation of previous from concomitant medications will be done by comparison of the stop date of the medication with the date of the first treatment with study medication. Each medication will be allocated unambiguously either to previous or concomitant medications:

- **Previous medication:** If the stop date is before start of treatment or the stop date is partially given and unambiguously before the start of treatment, the medication is allocated to previous medications.
- **Concomitant medication:** If the stop date is at or after the start of treatment or the medication is ongoing, the medication is referred to as concomitant medication. If the stop date is partially given and not unambiguously before start of treatment, the medication is allocated to concomitant medication. If the stop date is missing and the medication is not known to be ongoing, the worst case is assumed, and the medication is allocated to concomitant medication.

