8.1.10 Post-treatment Follow-up Period

All subjects discontinued from protocol-prescribed therapy for any reason will be followed for a period of [REDACTED] days after the last dose of IMP for AE reporting, as well as serious adverse events (SAEs) made known to the Investigator at any time thereafter that are suspected of being related to the IMP (FU1).

Beyond FU1, all subjects discontinued from protocol-prescribed therapy for any reason should be followed for state of condition/survival until the end of the follow-up period (refer to VII Schedule of assessments and procedures, part 3).

Females of child-bearing potential (FCBP) should avoid becoming pregnant for [REDACTED] after the last dose of IMP and male subjects should avoid fathering a child for [REDACTED] after the last dose of IMP.

Data regarding subsequent MDS/AML therapies and other malignancies/pre-malignancies as well as date and cause of death, if applicable, will be recorded in the eCRF. The investigator must make every effort to obtain information regarding the subject's survival status before determining the subject is lost to follow-up. If the subject is discontinued from follow-up, the reason for discontinuation should be recorded in the eCRF at EOS.

Follow-up may be conducted by telephone contact with the subject, family, or the subject's treating physician.

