**Part 3 – EOT and follow-up period (all patients)**

VISIT NO.	██████ ██████ ██████	███ ██████ ██████	██████████ ██████ ██████████ ██████████	██████	███ ██████
Study Day (± 3d)	██████	██████	██████	██████████	██████████
Study Week	██████	██████	██████	██████	██████
Informed consent					
In- / exclusion criteria 					
MDS/AML related medical history					
Concomitant MDS/AML specific medication	x	x	x	x	
Physical examination, vitals	x	x	x	x	
BMI	x	x	x	x	
Pregnancy test 	x	x	x	x	
Toxicity/AE assessment	x	x	x	x	
Quality of life (QoL, EORTC QLQ-C30)	x	x	x		
Information on current state of condition / survival status	x	x	x	x	x
Central assessments / correlative analyses (EU: Leipzig, AUS: QIMRB, Brisbane)					
Bone marrow aspiration (5 mL sodium heparinized in separate tubes for central assessments)		x 			
Peripheral blood sampling for central assessments (10 mL sodium heparinized blood in separate tubes for central assessments)		x 			
Genetic profiling (NGS) at central laboratories		x			
MRD analyses at central laboratories					
Telomere length & telomerase profiling at central laboratories		x			
Study-specific biomaterial collection		x			
Local assessments					
Serum chemistry (local)	x	x	x		
Automated CBC (local)	x	x	x		

 FU2/EOS can be carried out on the telephone

 To be carried out once the results of the response assessment from █████ are available and at the latest 14 days after the date of decision of treatment discontinuation

 Responders after the assessment at █████ will be treated further until loss of response/disease progression. In the case of safety issues, loss of response or disease progression, patients will undergo the EOT visit within 14 days from the date of decision of treatment discontinuation.

 BM and PB sample collection should only be performed at EOT visit if > 90 days from prior BM procedure

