## 7.3 Data Review

Data are checked and cleaned during the course of the study. Protocol deviations such as time window deviations are identified during monitoring and by data management checks. The statistical programmer will collect the protocol deviations. Additional protocol deviations might be identified and added during this data review.

Classification of protocol deviations into critical and non-critical will be discussed between Sponsor and statistician prior to database lock, with the final decision being made by the Sponsor. A critical protocol deviation is defined as protocol deviation which might influence the outcome of the primary analysis (e.g., a violation of eligibility criteria detected after enrolment). The free choice of subjects to terminate their study participation prematurely is described in the study protocol and thus not regarded as protocol deviation but as reason for exclusion from the per protocol set. The following list of criteria can be used to identify critical protocol deviations and is not meant to be exhaustive:

- Violation against eligibility criteria
- Deviation from visit window of primary endpoint visits.
- Assessment of primary endpoint not performed
- Use of disallowed concomitant medication

For further details it is referred to the Data Review Meeting Plan (DRM).

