### 8.2.3 Medical History, Concomitant Diseases/Procedures, Previous and Concomitant Medication

Absolute and relative frequencies (n, %) of concomitant disease will be summarized based on MedDRA system organ class (SOC) and preferred term (PT) levels for the SES.

Absolute and relative frequencies (n, %) concomitant medication and MDS/AML specific concomitant medication will be summarized based on Anatomical Therapeutic Chemical (ATC) Classification code levels 2 and 3 for the SES.

Absolute and relative frequencies (n,%) of MDS/AML related Medical History will be summarized for the SES.

All results will be presented by cohort (see 2.7).

Table	
14.3.1	Concomitant diseases by SOC and PT
14.3.2	MDS/AML related history
14.3.3	Concomitant medications by ATC levels
14.3.4	MDS/AML specific concomitant Medication by ATC levels
Listing	
16.3.1	Concomitant diseases
16.3.2	MDS/AML related history
16.3.3	Concomitant Medication
16.3.4	MDS/AML specific concomitant Medication
16.3.5	Medical history
16.3.6	Prior MDS/AML specific medication

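### SAP 7.5.4 sorts medication by stop date alone, so therapy started after imetelstat has ended is tabulated as concomitant, and no planned output shows subsequent therapy

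*SAP*

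**What the plan says.** SAP 7.5.4 says that the separation "will be done by comparison of the stop date of the medication with the date of the first treatment with study medication". The two classes are meant to be exhaustive: "Each medication will be allocated unambiguously either to previous or concomitant medications". A medication is previous if it stopped before first dose. Otherwise, "If the stop date is at or after the start of treatment or the medication is ongoing, the medication is referred to as concomitant". A missing stop date, or a partial one that is not clearly before first dose, also leads to concomitant.

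Therapy after imetelstat is collected. Protocol 8.1.10 has this entered in the eCRF during follow-up: "Data regarding subsequent MDS/AML therapies". Protocol 8.2.6.1 again provides for data on later MDS therapies. In Part 3 of the schedule (SAP 2.4 and protocol VII) the row "Concomitant MDS/AML specific medication" is marked in four of the five columns. The column headings are blacked out, but the pattern of assessments indicates that the row runs through the first follow-up visit and is blank at the last one.

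On outputs, SAP 8.2.3 says that "concomitant medication and MDS/AML specific concomitant medication will be summarized based on Anatomical Therapeutic Chemical (ATC) Classification code levels 2 and 3", for the safety set and by cohort. These are Tables 14.3.3 and 14.3.4. The variable list in SAP 6.1 has prior and concomitant MDS/AML drugs only. Neither SAP 8.2.3 nor the output list in SAP 11.1 contains a display of subsequent therapy.

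SAP 7.3 lists "Use of disallowed concomitant medication" among the criteria that may identify a critical protocol deviation.

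**The concern.** A reader will use Table 14.3.4 to see whether patients received other anti-leukemic drugs while on imetelstat. That bears on how response and toxicity are read. Under the printed rule the table answers a different question: whether a patient received such a drug at any time from first dose to the end of data collection. A prohibited drug given alongside imetelstat and a new treatment begun after imetelstat failed look the same.

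The second gap concerns overall survival. SAP 7.7.5 follows patients to death or last observation alive and does not censor at new therapy. That is a legitimate choice, but a survival curve of this kind in a single-arm study is hard to interpret without knowing how many patients in each cohort went on to other treatment. The data are to be recorded, yet no table or listing presents them as subsequent therapy.

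The situation is foreseeable. Patients without a response normally stop imetelstat and enter follow-up (protocol 5.1.3), and the SAP document history reports no responders at the interim analysis.

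**Working it through.** The plan states no figure on this point, so the check is a trace of the rule.

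**Step 1: the rule applied to a drug begun after imetelstat.** Let F be the first imetelstat dose, L the last, S the drug's start date and E its stop date. For such a drug S > L, and L ≥ F. Since E ≥ S, it follows that E > F. The branches of SAP 7.5.4 then give:

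| Stop-date information | Class under 7.5.4 |
|---|---|
| Known (E > F) | concomitant |
| Ongoing | concomitant |
| Partial (cannot be clearly before F) | concomitant |
| Missing, not known to be ongoing | concomitant |

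No branch gives another result.

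**Step 2: three drugs side by side.**

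| Drug | Timing | Class under 7.5.4 |
|---|---|---|
| A | E < F | previous |
| B | S between F and L | concomitant |
| C | S > L | concomitant |

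B and C differ only in S relative to L, and the rule uses neither.

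**Step 3: effect on Table 14.3.4.** In a cohort of N patients, let c have an anti-leukemic drug during imetelstat and s have one started afterwards. The number of patients shown with any concomitant MDS/AML drug lies between max(c, s) and min(N, c + s). If c = 0, the table shows s patients although the correct number is 0. With N as denominator, each patient who has only post-treatment therapy adds 1/N to the percentage. For assumed cohorts of 10, 20 or 40 this is 1/10 = 10, 1/20 = 5 or 1/40 = 2.5 percentage points per patient. Cohort sizes are blacked out and the documents give no rate of later therapy, so s cannot be estimated.

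**Step 4: where the label goes next.** No endpoint derivation in SAP 7.7 uses it. The FAS (SAP 4.1.1) requires at least one dose and fulfilled inclusion criteria, so it does not depend on the label either. The only possible link to an efficacy analysis is the disallowed-medication criterion in SAP 7.3, which may feed the PPS.

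**The case against.** **Subsequent therapy may sit on its own eCRF page.** Protocol 8.1.10 and 8.2.6.1 name it as a follow-up item, and the eCRF and mock layouts are not available. If so, 7.5.4 might never be applied to it. This stands in part: the mislabelling holds for therapy that is present in the medication data. But the schedule collects MDS/AML drugs under the concomitant heading after treatment has ended, and even a separate page has no planned output.

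**The tables are background.** They fall under SAP 8.2, on characteristics not related to the objectives, and all analyses are exploratory (protocol 10.1). That stands, and it limits the weight of the point.

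**A reader might infer that the rule pushes non-responders out of the PPS and raises the PPS response rate.** The text that invites this is Appendix VII of the protocol, which prohibits other anti-leukemic treatment for the duration of the study, and SAP 7.3, whose medication criterion carries no time limit. The documents do not support the inference:
- SAP 7.3 defines a critical deviation as one that might influence the primary analysis. Therapy begun after the visit 9 assessment cannot change a response already determined from that visit's samples.
- The criteria list is optional, and the sponsor decides after discussion with the statistician. The PPS is settled patient by patient (SAP 4.1.2).
- Patients who leave before the required week are outside the PPS in any case.
- With no responders, as at the interim analysis, the rate is 0% whoever is excluded.
- Protocol 7.9.3 on concomitant medication is blacked out and may contain a time limit.

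What remains is a possible misreading of SAP 7.3 that one sentence would close.

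**Conclusion.** The point holds for the tabulation and for the missing output. As printed, SAP 7.5.4 classes every drug started after the last imetelstat dose as concomitant. Tables 14.3.3 and 14.3.4 therefore cannot separate treatment given with imetelstat from treatment given after it. This follows from the stated rule and needs no numerical assumption beyond the drug being in the medication data. No planned display shows subsequent MDS/AML therapy, although it is to be collected and is needed to read overall survival.

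The FAS response result, the survival estimates and the other endpoint derivations are unaffected. An effect on the PPS is a possible risk in the deviation review and not an automatic exclusion, so no figure for a raised PPS rate can be given. The change is worth making before database lock because a planned safety-set table would otherwise mislead.

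**What to change.** 1. In SAP 7.5.4, use the start date as well and define three classes: previous (stopped before first dose), concomitant (taken at any time between first and last imetelstat administration) and post-treatment (started after the last imetelstat administration).
2. Restrict Tables 14.3.3 and 14.3.4 to the concomitant class.
3. Add one table or listing of subsequent MDS/AML therapy by cohort, and name it in SAP 6.1, 8.2.3 and 11.1.
4. As a secondary clarification, state in SAP 7.3 that only disallowed medication taken between first dose and the primary-endpoint assessment counts towards PPS exclusion. This concerns the analysis set only and leaves the protocol's list of prohibited drugs as it is.

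Protocol 10.6 gives previous and concomitant only as examples of medication types, so a third class fits it, and SAP 2.10 allows such an update before database lock. The cost is one derived flag, one extra output and a convention for partial or missing start dates. In keeping with the present rule, a start date that is not clearly after the last dose could default to concomitant. That medication start dates are collected is an assumption, since the documents do not say so; it should be confirmed against the eCRF first.

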## 7.6 Rounding Rules

### 7.6.1 Estimates of the Mean and Standard Deviation

When using reported data, the mean and standard deviation will both be calculated to the least precise range.

When using data derived/calculated from reported data, the mean and standard deviation will both be calculated to at least two (2) extra digits more than the reported data and the result will be rounded to one more decimal place than the reported data. The rounding of the extra digits will be done according to the following rules (as conducted by default in SAS):

- If the second extra digit is less than five (5), it is dropped.
- If the second extra digit is greater or equal five (5), it is dropped, and the first extra digit is increased by one (1).

### 7.6.2 Other data

Quartiles, confidence intervals (CIs) and median will be presented with the same number of decimal places as the mean. Minimum and maximum will be presented with the same number of decimal places as the data used. For estimates of proportions, the result will be rounded to 3 decimal places. If proportions are displayed as percentage, 1 decimal place will be displayed. For example, a proportion of 0.655 will be presented in percentage as 65.5%.

## 7.7 Data Derivation

This section describes rules for the derivation of variables not directly recorded in the eCRF. Derived variables will be marked in subject data listings by “#” in the listing header.

### 7.7.1 Baseline Definition and Change from Baseline

In general, the baseline value of an assessment is defined as the last available measurement before start of treatment. For vital signs (except for height, weight and BMI), physical examination, serum chemistry and automated CBC, baseline is the last available measurement before visit 1 (cycle 1, week 1). For the remaining variables baseline values are collected at the screening visit.

Change from baseline will be calculated as follows only for continuous variables:

$$\text{Change from baseline} = (\text{post-baseline value}) - (\text{baseline value})$$

### 7.7.2 Transfusion History

#### Number of units within ■ weeks before treatment

The number of units within ■ weeks will be defined as the sum of all units of the same type (RBC or platelets) transfused before and including the date of the first IMP administration, i.e., all transfusions dated in the interval [DA ■ days, DA ■] where:

$$\text{DA } \blacksquare = \text{Drug administration date of } \blacksquare \text{ [YYYY-MM-DD]}$$

#### Number of units after first dose

The number of units after first dose will be defined as the sum of all units of the same type (RBC or platelets) transfused between the date of IMP administration and the date of study discontinuation (SD).

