The study will consist of a screening period, a primary treatment period (all patients), an extension treatment period (responders after 4 cycles of treatment only) and a posttreatment follow-up period. For the extension treatment period, in the absence of alternative treatment options, non-responders with stable or controlled disease may continue treatment at the investigator's discretion, in consultation with the sponsor, provided the disease remains controlled and none of the discontinuation criteria as described in section 7.7 are met.

[figure not shown]
Patients who stop the study treatment for any cause will undergo an EOT visit at the latest 14 days after the decision of treatment discontinuation. The EOT visit will be followed by a first follow-up visit (FU1) 28 ± 5 days after EOT and a second FU visit = EOS visit approximately 2 months after EOT. FU2/EOS can be carried out on the phone and represents the last study visit for the patient.

The End of Study is considered at the time the last patient completed their evaluation 6 months after the end of the primary treatment period (in case of a continued responder) or following their follow-up period (in case of a non-responder). For avoidance of doubt, for non-responders with stable or controlled disease who continue treatment at the investigator's discretion, the end of study will be defined as the end of the follow-up period for said patient or discontinuation from the trial, whichever occurs later. The sponsor will ensure that subjects benefiting from treatment with imetelstat will be able to continue treatment for as long as the subject's disease is controlled, provided that an adequate stock of imetelstat is available.

A summary of the study design is given in Figure 1.

For detailed description of study visits and procedures see VII Schedule of assessments and procedures and section 8.2.

Figure 1: Study flowchart

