8.2.4.2 Transfusion data collection and assessment

All transfusions received in a time window of 16 weeks preceding the first IMP administration will be collected in the eCRF for subsequent HI assessments.

During the study, all received transfusions will be collected in the eCRF.

For transfusions, the following should be documented:

- type of transfusion (e.g., pRBC or platelet)
- number of units
- reason for transfusion
- date of transfusion
- Hb value for which any RBC transfusion is given (i.e., pretransfusion Hb)
- platelet value for which any platelet transfusion is given

Clinical site staff should confirm if any transfusions were received by the subject (including any at outside local institutions in between study visits) prior to each IMP administration via use of patient diary or other local procedure in place at the investigational site.

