The study will consist of a screening period, a primary treatment period (all patients), an extension treatment period (responders after 4 cycles of treatment only) and a posttreatment follow-up period. For the extension treatment period, in the absence of alternative treatment options, non-responders with stable or controlled disease may continue treatment at the investigator's discretion, in consultation with the sponsor, provided the disease remains controlled and none of the discontinuation criteria as described in section 2.1.8 are met.

[figure not shown]
Patients who stop the study treatment for any cause will undergo an EOT visit at the latest 14 days after the decision of treatment discontinuation. The EOT visit will be followed by a first follow-up visit (FU1)  $28 \pm 5$  days after EOT and a second FU visit = EOS visit approximately 2 months after EOT. FU2/EOS can be carried out on the phone and represents the last study visit for the patient.

The End of Study is considered at the time the last patient completed their evaluation 6 months after the end of the primary treatment period (in case of a continued responder) or following their follow-up period (in case of a non-responder). For avoidance of doubt, for non-responders with stable or controlled disease who continue treatment at the investigator's discretion, the end of study will be defined as the end of the follow-up period for said patient or discontinuation from the trial, whichever occurs later. The sponsor will ensure that subjects benefiting from treatment with imetelstat will be able to continue treatment for as long as the subject's disease is controlled, provided that an adequate stock of imetelstat is available..

A summary of the study design is given in Figure 1.

For detailed description of study visits and procedures see 2.4.

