### 2.1.8 Treatment discontinuation

All subjects will have an End of Treatment (EOT) visit at the time of imetelstat discontinuation. All subjects who received at least one dose of imetelstat will be followed for 3 months post last dose of imetelstat.

The following events are considered sufficient reasons for discontinuing a subject from treatment with the IMP:

- Lack of efficacy
- Adverse event
- Withdrawal by subject
- Death
- Lost to follow-up
- Pregnancy
- Protocol violation
- Study terminated by Sponsor
- Disease Progression as per combined response criteria based on IWG 2018 criteria (MDS) and the criteria of the European LeukemiaNet (AML)
- Other (to be specified on the eCRF)

The reason for discontinuation of treatment should be recorded in the eCRF and in the source documents. The decision to discontinue a subject from treatment remains the responsibility of the treating physician, which will not be delayed or refused by the sponsor. However, prior to discontinuing a subject, the investigator may contact the sponsor and forward appropriate pseudonymized supporting documents for review and discussion.

Subjects who discontinue from treatment for any reason will enter the follow-up period (for details refer to section 2.4 Trial Schedule and section 2.1.5 Posttreatment follow-up (FU) period).

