### Rates

The respective transfusion rates will be defined as the number of units in each period divided by the number of days in the period, i.e., ■ days before treatment and  $TD [days] = SD - DA$  ■ after first dose.

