#### **7.7.3 Duration of treatment**

Duration of treatment (DoT, in days) will be defined as the time elapsed from the start of treatment (date of administration at cycle ■, week ■) to the date of treatment discontinuation (TD) or the last available date with drug administration (LD):

$DA$  ■ = Drug administration date in Visit ■ [YYYY-MM-DD]

$DoT [days] = \min(TD, LD) - DA$  ■

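### The post-dose transfusion rate runs to study discontinuation, so Table 14.10.1 mixes on-drug and follow-up time and does not show transfusion need on treatment

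*SAP*

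**What the plan says.** SAP 7.7.2 defines two periods for each transfusion type (RBC, platelets). The baseline period covers units "transfused before and including the date of the first IMP administration"; SAP 8.6 gives its length as 16 weeks. The post-dose period covers units "transfused between the date of IMP administration and the date of study discontinuation (SD"). Under Rates the SAP states: "The respective transfusion rates will be defined as the number of units in each period divided by the number of days in the period". For the post-dose period the divisor is SD minus the first-dose date.

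The end of treatment is a different date in the same SAP. Section 7.7.3 measures duration of treatment "to the date of treatment discontinuation (TD) or the last available date with drug administration (LD"), taking the earlier of the two.

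The time between treatment end and study end is described in two ways:

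- SAP 2.1 places the "EOT visit at the latest 14 days after the decision of treatment discontinuation", and Protocol 5.1 then has "a second FU visit = EOS visit approximately 2 months after EOT".
- SAP 2.1.8, like Protocol 7.7, says that dosed subjects "will be followed for 3 months post last dose of imetelstat". The time plan in the protocol synopsis also gives 3 months of follow-up.

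Protocol 8.1.10 provides for recording later MDS/AML therapies in this period.

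SAP 8.6 summarises units, rates and pretransfusion levels in the FAS by transfusion type, for before treatment and after first dose, by cohort (Table 14.10.1). Protocol 10.8.3 had planned descriptive statistics by visit. SAP 8.6 keeps the by-visit data only as a listing, and SAP 9 does not mention this change.

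**The concern.** Anyone reading Table 14.10.1 will set the two rates against each other and take the difference as the change in transfusion need under imetelstat. The baseline rate covers 16 untreated weeks. The post-dose rate averages treated weeks with weeks after treatment has stopped, when the patient may have progressed, may be recovering from drug-related cytopenia, or may be on another therapy.

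The weight given to off-drug time also depends on outcome. It is largest for patients who stop early and nil for those still on drug at study end. Two cohorts with different time on drug can therefore show different rates even if need on treatment is the same. Off-drug time is likely to be common in cohort 1: the SAP document history records no responders at the interim analysis, and under the regimen then in force (Protocol 7.1.1) non-responders went to EOT and follow-up. No on-treatment version or sensitivity analysis is planned.

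A smaller point sits in the same section. The baseline interval explicitly includes the first-dose date, and the post-dose definition does not say whether it does, so a unit given that day could be counted in both.

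**Working it through.** The documents state no transfusion rate, so there is no figure to reproduce. The check is person-time arithmetic.

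**Inputs**

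- Time on drug, T_on: 56 days for a patient stopped at the early assessment (visit 5, week 9 in SAP 8.3) and 112 days for one stopped at the primary assessment (visit 9, week 17). Dosing continues until assessment results are available, so true values can be slightly longer. For contrast: 183 and 365 days.
- Time off drug, T_off: 61 days (2 months from EOT to EOS); 75 days (61 plus the maximum 14-day lag to EOT); 91 days (3 months after last dose).
- a = on-drug transfusion rate relative to baseline. a = 1 means no drug effect.
- k = off-drug rate relative to baseline. The documents do not give it, so it is an assumption, shown over a range.

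**Step 1. Off-drug share of the post-dose window** = T_off / (T_on + T_off)

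| T_on | T_off 61 | T_off 75 | T_off 91 |
|---|---|---|---|
| 56 | 61/117 = 52% | 75/131 = 57% | 91/147 = 62% |
| 112 | 61/173 = 35% | 75/187 = 40% | 91/203 = 45% |
| 183 | 25% | 29% | 33% |
| 365 | 14% | 17% | 20% |

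**Step 2. After/before rate ratio as SAP 7.7.2 defines it** = (a·T_on + k·T_off) / (T_on + T_off)

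No drug effect (a = 1), 112 days on, 61 off:

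- k = 0.5: (112 + 30.5)/173 = 0.82
- k = 1: 173/173 = 1.00
- k = 2: (112 + 122)/173 = 1.35

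With 91 days off, k = 0.5 gives 0.78 and k = 2 gives 1.45. With 56 days on and 61 off, k = 0.5 gives 0.74 and k = 2 gives 1.52.

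True halving on drug (a = 0.5), 112 days on, 61 off:

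- k = 1: (56 + 61)/173 = 0.68
- k = 2: (56 + 122)/173 = 1.03

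So a drug with no effect can appear to change transfusion need in either direction, and a real halving can disappear.

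**Step 3. The same ratio with the window closed at treatment end** = a·T_on / T_on = a, whatever k is: 1.00 with no effect and 0.50 with a true halving.

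**The case against.** The strongest reply is that this is a descriptive side-by-side table in a study whose analyses are all exploratory (Protocol 10.1). Transfusion burden is among the other endpoints of SAP 6.2.3; there is no test, change score or decision rule. Following patients to study end regardless of discontinuation is also a recognised treatment-policy summary. An on-treatment cut-off has its own bias: it drops transfusions after failure and can flatter the drug. Not all off-drug time is unrelated to imetelstat either. Protocol 9.3 collects adverse events until 28 (±5) days after EOT, and cytopenias are the main toxicity. These arguments stand. They are reasons to keep the present rate beside an on-treatment rate, not reasons to leave the on-treatment rate out.

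Size and frequency are also limited. The 14-day lag is a maximum, and k is assumed; at k = 1 a null drug shows exactly 1.00. Protocol 1.1.1 cites a median survival of 4–5.6 months in higher-risk MDS after HMA failure, so many patients may not complete follow-up. Some non-responders with stable or controlled disease may now continue treatment. This stands, and limits the point to patients who stop and are then followed.

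A reader might infer three stronger things that the documents do not support:

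- *That off-drug transfusions go unrecorded.* The sentence beginning "Clinical site staff should confirm if any transfusions were received by the subject" ties that check to each imetelstat administration, and the follow-up schedule has no transfusion row. But the same section requires every transfusion during the study to be entered in the eCRF, and no part of the schedule has such a row. Weaker capture in follow-up is a fair worry, particularly as the last visit may be by telephone; zero capture is not what the plan says.
- *That first-dose-day units are certainly counted twice.* The post-dose wording is ambiguous, and a divisor of SD minus first-dose date without adding a day fits a period that starts the day after.
- *That transfusion response as a whole is compromised.* HI-E, within the primary endpoint, uses transfusion data in its own windows (Protocol Appendix III a) and does not use this rate.

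**Conclusion.** The point holds for patients who stop imetelstat and are then followed. For them the post-dose rate combines on-drug time with about 2 to 3 months off drug: 35–45% of the window after 112 days on drug and 52–62% after 56 days. These shares rest on the visit timings in the documents and on follow-up being completed.

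The effect on the after/before ratio rests on the assumed off-drug rate and has no fixed sign. For a null drug with 112 days on and 61 off, it is 0.82 to 1.35 as off-drug need goes from half to twice baseline. What can be said without that assumption is that the tabulated rate does not measure transfusion need on treatment, and that its off-drug weight varies with time on drug and so may differ between cohorts. The matter is confined to a descriptive, exploratory table. It is an inexpensive improvement, not a threat to the trial's main conclusion.

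**What to change.** In SAP 7.7.2 and 8.6:

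- Add an on-treatment rate as the main summary. Start both units and days on the day after first dose, which also removes the possible double count. End both at one stated treatment-end date, such as the EOT visit or the 7.7.3 treatment-end date plus one dosing interval, or at the start of other MDS/AML therapy if that is earlier and dated.
- Show the rate for the follow-up period separately.
- Keep the rate to study discontinuation as supportive, so that transfusions after failure or for late cytopenia stay visible.
- Rename the elapsed time called TD under Rates, since 7.7.3 uses TD for a date.
- Record the move away from by-visit summaries in SAP 9, and reconcile the 2-month and 3-month descriptions of follow-up.

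SAP 2.10 allows such a change by SAP update before database lock. The cost is a few lines of text, an end-date variable and one or two extra rows per transfusion type. The treatment-end dates are already defined; whether start dates of later therapy are captured should be confirmed, because Protocol 8.1.10 does not say so. The downside is that the on-treatment rate does not reflect need after failure, which is why the other two rates stay in the table.
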